7.8.1.2 Analysis of other significant AEs

Other significant AEs will be reported and summarised according to ICH E3 criterion (9.5). Thus, AEs classified as 'other significant' will include those non-serious adverse events with 'action taken = discontinuation' or 'action taken = dose reduced'.

7.8.1.3 AE summaries

An overall summary of adverse events will be presented.

The frequency of patients with adverse events will be summarised by treatment, primary SOC and PT. The SOC and PTs will be sorted by frequency (within SOC). AEs which were defined as secondary endpoints will be summarised separately. AEs will also be reported by intensity according to the maximum Common Terminology Criteria for Adverse Events (CTCAE). Separate tables will be provided for patients with other significant AEs according to ICH E3 (9.5), for patients with serious adverse events, for patients with AEs leading to dose reduction, for patients with AEs leading to discontinuation, for patients with AEs leading to death, for patients with drug-related AEs, and drug-related serious AEs.

For further details on summarisation of AE data, please refer to "Handling of missing and incomplete AE dates" (9.2) and "Analysis and Presentation of Adverse Event data from Clinical Trials" (9.6).

7.8.1.4 AEs of special interest (AESIs)

The protocol defines the following adverse event as AESI:

• Hepatic injury:

A hepatic injury is defined by alterations of the hepatic laboratory and clinical parameters after randomisation as detailed by the removal and stopping criteria in CTP Section 3.3.4.1 and CTP Appendix 10.2.

An independent Adjudication Committee will adjudicate certain hepatic events for the severity and causal relationship with the trial medication. Adjudication assessments will be incorporated to the database. Frequency tables will be provided for the PTs in the specified SMQs of events and for the adjudication endpoints. Tables will be provided for events qualifying for adjudication and then separately the events that were confirmed or non-assessable.

7.8.1.5 User-defined adverse event category (UDAEC)

UDAEC will be summarized by dose group, primary system organ class and preferred term. In summary, Table 7.8.1.5:1 provides the definition of UDAECs according to AE category or Standardized MedDRA Query (SMQ).

Proprietary confidential information © 2024 Boehringer Ingelheim International GmbH or one or more of its affiliated companies.

Table 7.8.1.5: 1	Definition of continuous UDAEC
------------------	--------------------------------

Category	Safety topic	Definition		
UDAEC	Hypotension	Investigator-reported, as a dedicated AE category on the AE eCRF page		
UDAEC	Syncope	Investigator-reported, as a dedicated AE category on the AE eCRF page		
UDAEC	Acute kidney injury	SMQ 'Acute renal failure', narrow scope		
UDAEC	Peripheral edema	SMQ 'Haemodynamic oedema, effusions and fluid overload'		
UDAEC	Bleeding	SMQ 'Haemorrhages', narrow scope		
UDAE	Liver events	Narrow sub-SMQ 'Liver related investigations, signs and symptoms', narrow sub-SMQ 'Cholestasis and jaundice of hepatic origin', narrow sub-SMQ 'Hepatitis, non-infectious' and narrow sub-SMQ 'Hepatic failure, fibrosis and cirrhosis and other liver damage-related conditions'		

Summary of hypotension and syncope will be presented for both patient-based and eventbased analyses.

Analysis on hypotension based on baseline BP and the lowest BP during the episode will be carried out. Criteria for significant (vs. non-significant) hypotensive episode are:

- -
- Baseline SBP <=140: decrease $\left(\frac{\text{lowest SBP during the episode baseline SBP}}{\text{baseline SBP}}\right) \ge 30\%$; Baseline SBP >140: decrease $\left(\frac{\text{lowest SBP during the episode baseline SBP}}{\text{baseline SBP}}\right) \ge 40\%$; -
- Or, lowest SBP during the episode <90. _
- Baseline DBP <=70: $\left(\frac{\text{lowest DBP during the episode baseline DBP}}{\text{baseline DBP}}\right) \ge 30\%$; Baseline DBP > 70: $\left(\frac{\text{lowest DBP during the episode baseline DBP}}{\text{baseline SBP}}\right) \ge 40\%$; _
- _
- Or, lowest DBP during the episode <50. _
- Lowest mean arterial pressure (MAP = DP + 1/3(SP DP)) during the episode<70. _

The severity of hypotension will be categorised based on the CTCAE grades collected from the eCRF:

- CTCAE grade 1 mild -
- CTCAE grade 2 moderate
- CTCAE grade 3, 4 or 5 severe

c43185880-01

Proprietary confidential information © 2024 Boehringer Ingelheim International GmbH or one or more of its affiliated companies.

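### SAP 7.8.1.5: the criterion for baseline DBP above 70 divides a diastolic fall by baseline SBP, so some diastolic falls of 40% or more from a baseline DBP of 84 or higher are classed as non-significant

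*SAP*

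**What the plan says.** SAP Section 7.8.1.5 (User-defined adverse event category) plans an analysis of hypotension from baseline blood pressure and the lowest pressure during the episode, and lists what makes an episode significant. The quotes below stop just before the per cent sign.

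Relative criteria:

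- For lower systolic baselines the SAP prints "Baseline SBP <=140: decrease $\left(\frac{\text{lowest SBP during the episode baseline SBP}}{\text{baseline SBP}}\right) \ge 30" as its rule.

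- For higher systolic baselines it prints "Baseline SBP >140: decrease $\left(\frac{\text{lowest SBP during the episode baseline SBP}}{\text{baseline SBP}}\right) \ge 40" instead.

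- For lower diastolic baselines the rule is "Baseline DBP <=70: $\left(\frac{\text{lowest DBP during the episode baseline DBP}}{\text{baseline DBP}}\right) \ge 30" in the same form.

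- For higher diastolic baselines, the line at issue here, it is "Baseline DBP > 70: $\left(\frac{\text{lowest DBP during the episode baseline DBP}}{\text{baseline SBP}}\right) \ge 40" with a systolic denominator.

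Absolute criteria:

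- The systolic limit is given as "Or, lowest SBP during the episode <90" (mmHg).

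- The diastolic limit is given as "Or, lowest DBP during the episode <50" (mmHg).

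- A third limit, on mean pressure, is given as "Lowest mean arterial pressure (MAP = DP + 1/3(SP DP)) during the episode<70" (mmHg).

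Severity is handled separately: "The severity of hypotension will be categorised based on the CTCAE grades collected from the eCRF".

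SAP Section 4 withdraws the HVPG analyses and the intercurrent-event reporting after the programme was stopped. It does not withdraw this hypotension analysis.

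**The concern.** The last relative criterion mixes two pressures: a diastolic change over a systolic baseline. Nothing in the SAP or the protocol defines or explains such a ratio, and the three parallel lines do not use it.

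This line should govern most participants. Exclusion criterion 7 (protocol Section 3.3.3) removes anyone with a screening DBP below 70. SAP Section 6.7 takes baseline as the last value before first dose, so some baselines may drift to 70 or lower, but most should lie above it.

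Hypotension is the mechanism-related risk of this drug (protocol Sections 1.4.2 and 3.2). A rule that under-counts significant episodes errs in the unhelpful direction. With few participants treated, a single reclassified episode would show in the table.

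**Working it through.** **Inputs.** The criteria are those of SAP 7.8.1.5, read as alternatives. Pressures are in whole mmHg (protocol Section 5.2.2). The SAP gives no worked result for this rule, so there is no figure to reproduce. Each relative criterion is taken as a fall, baseline minus lowest.

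**1. Denominators side by side**

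| Criterion | Change in | Divided by | Cut-off |
|---|---|---|---|
| Baseline SBP ≤ 140 | SBP | baseline SBP | 30% |
| Baseline SBP > 140 | SBP | baseline SBP | 40% |
| Baseline DBP ≤ 70 | DBP | baseline DBP | 30% |
| Baseline DBP > 70 | DBP | **baseline SBP** | 40% |

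**2. Direction of the error.** Write S and D for baseline SBP and DBP, and d for the lowest DBP.

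- Like-for-like denominator: (D − d)/D ≥ 0.40, so d ≤ 0.6 × D.
- As printed: (D − d)/S ≥ 0.40, so d ≤ D − 0.4 × S.

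Since S > D, the printed trigger is always the lower one. It can miss episodes but cannot add any.

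**3. Step at the branch boundary, SBP 120**

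- D = 70: fall of 0.3 × 70 = 21 mmHg needed (to 49).
- D = 71, as printed: 0.4 × 120 = 48 mmHg (to 23).
- D = 71, like for like: 0.4 × 71 = 28.4 mmHg (to 42.6).

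One mmHg of baseline more than doubles the required fall. This is evidence of a slip. It is not itself a misclassification, because the rule for DBP below 50 already flags these falls.

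**4. Where the class changes.** 0.6 × 83 = 49.8, so for baselines 71 to 83 every 40% fall ends below 50 and is flagged anyway. 0.6 × 84 = 50.4, so from 84 a 40% fall can end at 50 or above.

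| Baseline | Trigger, like for like (0.6 × D) | Trigger, printed (D − 0.4 × S) | Lowest DBP that can change class |
|---|---|---|---|
| 120/80 | 48 | 32 | none |
| 130/85 | 51 | 33 | 50–51 |
| 130/90 | 54 | 38 | 50–54 |
| 140/95 | 57 | 39 | 50–57 |

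Mean arterial pressure must also stay at 70 or more. If the lowest SBP and DBP come from one reading, (2 × DBP + SBP)/3 ≥ 70 gives SBP ≥ 210 − 2 × DBP: 110 at DBP 50, 108 at 51, 102 at 54.

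**5. Worked cases**

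- 140/95 to 115/55: DBP fall 40/95 = 42.1%, scored as 40/140 = 28.6%. SBP fall 25/140 = 17.9%. MAP = 55 + 60/3 = 75. Lowest SBP is not below 90 and lowest DBP is not below 50. No printed criterion is met.
- 130/84 to 110/50: DBP fall 34/84 = 40.5%, scored as 34/130 = 26.2%. SBP fall 20/130 = 15.4%. MAP = (100 + 110)/3 = 70.0. No printed criterion is met. At this fall the printed line would fire only if baseline SBP were at most 34/0.40 = 85.

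**6. Enumeration.** All whole-mmHg combinations were classified both ways, treating each episode as one reading: baseline SBP 100 to 180, baseline DBP 71 to 120, pulse pressure at least 10. The first class change is at baseline DBP 84. No episode was significant as printed but non-significant with the like-for-like denominator.

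**7. What the printed line adds.** It goes beyond the rule for DBP below 50 only if D − 0.4 × S ≥ 50, that is D ≥ 50 + 0.4 × S: 98 at SBP 120, 102 at 130, 106 at 140. The line is close to inert.

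**The case against.** **The effect is small.** This stands. A class change needs a baseline DBP of 84 or more, a lowest DBP in a narrow band, and no other criterion met. The planned size was 40, and the SAP says no subject completed 8 weeks. The split is descriptive, and no affected episode is shown to be likely.

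**The formula block is damaged in the available text.** Minus signs are missing from the numerators and from the MAP definition, so the denominator might also be an extraction fault. That is possible in principle. But lost symbols are a common conversion fault, while a whole term swapped in one of four parallel formulas is much more likely to be an error in the SAP. Checking the source file would settle it.

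**A programmer must interpret these lines anyway.** Both diastolic lines put lowest before baseline and omit the word decrease that the systolic lines carry. With a minus sign restored, a fall would come out negative. Whoever fixes the sign by analogy may fix the denominator too. That may happen, but a derivation rule should not depend on it.

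**The systolic limits in step 4 assume one reading.** This is correct. From baseline 130/84, readings of 105/60 (MAP 75) and 115/50 (MAP 71.7) leave the lowest SBP at 105, below the stated 110, yet no printed criterion is met. The window is therefore slightly wider than those limits suggest, and the conclusion is unaffected.

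**The alternatives reading is not explicit.** The word Or is printed only before the two absolute pressure lines. The threshold of 84 depends on reading all the lines as alternatives.

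**Conclusion.** The concern holds. The line for baseline DBP above 70 is inconsistent with its three counterparts and is wrong as a derivation rule. With whole-mmHg readings and criteria read as alternatives, no class changes for baseline DBP 71 to 83. From 84 upward, falls of 40% or more that end at a DBP of 50 or higher are missed when no systolic or MAP criterion is met. The error only under-counts.

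Its reach is limited to this one descriptive split. CTCAE severity and the secondary endpoints in protocol Section 2.1.3 do not use the formula. The documents give no baseline DBP distribution, so the number of affected episodes cannot be estimated and may be zero. It should still be corrected, because the table is still due and the correction costs almost nothing.

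**What to change.** In SAP Section 7.8.1.5 and in the derivation program, change the denominator of the line for baseline DBP above 70 from baseline SBP to baseline DBP. Leave the 30% and 40% cut-offs and all absolute thresholds unchanged. Confirm the denominator against the SAP source file first. In the same edit it would help to state that both diastolic lines refer to a decrease, and that the criteria are alternatives.

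The cost is one term in the SAP and one in the program, with no new data.

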7.8.2 Laboratory data

The analyses of laboratory parameters will be descriptive in nature and will be based on BI standards (9.7). Note that data from the central Laboratory will be used for all displays described below, unless otherwise specified.

For continuous safety laboratory parameters standardized and normalized values will be derived as well as the differences to baseline. Normalisation means transformation to a standard unit and to a standard reference range. The process of normalisation, handling of repeat values at the same visit for by-visit displays, as well as standard analyses for safety laboratory data are described in the BI guidance for "Handling, Display and Analysis of Laboratory Data" (9.7). All analyses considering multiple times of the ULN (as described below) will be based on standardised and not normalised values.

Laboratory parameters will be shown in conventional units. Where conventional units differ from SI units, analyses will be repeated on SI units in the appendix.

Laboratory values will be compared to their reference ranges and frequency tables will be provided for the number of patients within and outside the reference range at baseline (see Section 6.7) and the last measurement on treatment. Descriptive statistics will be provided by treatment group for baseline, last value on-treatment and for changes from baseline to last value on treatment. Frequency tables will summarise the number of patients with potentially clinically significant abnormalities.

Additionally, graphical analysis of the following lab parameters over time until EOS will be performed:

- Haemoglobin
- RBC count / erythrocytes
- WBC count / leukocytes
- Platelet count / thrombocytes
- Reticulocytes
- PT/INR
- ALT
- Alkaline phosphatase
- AST
- Bilirubin (total)
- Albumin
- Gamma-GT
- eGFR

Only patients with at least one available on-treatment value will be included in the analysis of an individual laboratory parameter. All individual data will be presented in listings.

To support analyses of liver related adverse drug effects, the frequency of patients with AST and/or ALT \ge 3xULN combined with the total bilirubin \ge 2xULN in 30 days period after AST/ALT elevation will be displayed, stratified by alkaline phosphatase < 2xULN and \ge 2xULN (a patient can potentially be in both alkaline phosphatase strata in case of multiple

c43185880-01

Proprietary confidential information © 2024 Boehringer Ingelheim International GmbH or one or more of its affiliated companies.

AST/ALT and bilirubin elevations). The start of the 30-day time span is triggered by each liver enzyme elevation above defined thresholds. This analysis will be based on standardised laboratory values.

A graphical analysis of the ALT and total bilirubin during the on-treatment period will also be performed; the so called eDISH plot. In the graph, for each subject, the peak total bilirubin is presented as a fold increase over the ULN against the peak ALT as a fold increase over the ULN, on a log 10 scale. The measurements displayed or total bilirubin and ALT may, or may not, occur on the same date. Two reference lines, 2xULN for total bilirubin and 3xULN for ALT, are drawn onto the graph in order to divide the plane into four quadrants. Normal cases are in the lower left quadrant, potential DILI cases are in the upper right quadrant (Hy's Law quadrant), while the lower right quadrant is known as the Temple's corollary range (ALT \geq 3xULN and total bilirubin < 2xULN). The same graphical analysis will be repeated on AST and total bilirubin. Details on patients with elevated live enzymes will be listed.

Clinically relevant findings in laboratory data will be reported as baseline conditions (at screening) or as AEs (during the trial). If judged clinically relevant by the investigator and will be analyzed as such.

7.8.3 Vital signs

The analyses of vital signs (blood pressure, pulse rate) will be descriptive in nature. Descriptive statistics of vital signs over time (pre-dose, 1 hour, 2 hours) and for the difference from baseline and pre-dose (see Section 6.7) will be provided by treatment within a study period as described in Table 6.1:1. Figures for change from baseline and change from pre-dose for both on-treatment visit and post-treatment visit will be provided as well.

7.8.4 ECG

Abnormal findings in 12-lead ECG will be reported as baseline conditions (at screening) or as AEs (during the trial) if judged clinically relevant by the investigator and will be analysed as such.

No separate listing or analysis of ECG data will be prepared.

